**Testing Products to Increase Children's Physical Activity in the Classroom: Identifying
What Works and What Doesn't**

Identifiers:NCT03394846 Unique Protocol ID: Pro00069012

5/26/2022

Study setting and participants

Study protocols were approved by the [REDACTED] IRB prior to enrollment of the first participant. Data were collected from five elementary schools in two separate school districts. Both school districts served a major metropolitan area in one southeastern state in the United States. Table 1 presents the participating schools' characteristics. These schools were identified to participate because they served a large number of minoritized children from families that are low income. These students often experience disproportionately fewer opportunities to participate in PA [18]. At regularly scheduled faculty meetings, teachers in the participating schools were provided with information about the study and invited to participate. Teachers who agreed to participate were provided with and signed an informed consent form. A total of 57 (60%) of teachers consented. For students in the consented teachers' classes, a passive consent procedure was employed due to the noninvasive and low-risk nature of the study. Letters with information about the study were sent home to the parents of children in the participating classes. If a parent did not wish for their child to participate, the letter informed them to sign and return the form to their child's classroom teacher. A total of 123 (5.2%) parents opted out of their child wearing the activity monitor. Prior to data collection, all children provided verbal assent.

Study design/procedure

The COVID-19 pandemic impacted this study and caused changes to the design. Prior to the COVID-19 pandemic, this pre-post study was designed to assess teachers' intact classrooms for a total of five weeks, at two separate timepoints in the spring (i.e., January and February) and fall (September and October) of 2020. The intention was to provide all teachers with three MI products to test in their classroom for one week each. The teachers would also be observed for

one week (i.e., baseline) when they were asked to go about their regularly scheduled classroom activities like any other typical week. The decision was made not to include a comparison group of teachers based on feedback from school administrators indicating they desired all participating teachers to receive a MI product and would not participate if that was not the case. One baseline week was allocated for the spring and fall. Following the baseline week, teachers were to receive one MI product to use (i.e., intervention). Teachers were to try one MI product in the spring and two products in the fall. The order of product testing was counterbalanced at the school level to minimize contamination and potential timing effects. However, due to disruptions of the COVID-19 pandemic, the study was not able to be executed as designed, and the provision of the MI products and measures were not completed in the fall of 2020. Thus, we collected one baseline week and one intervention week in spring of 2020, prior to the onset of the COVID-19 pandemic related school closures. This meant that each school only received one MI product for testing (see Table 1 for the product that each school tested).

The intention of this study was to maximize ecological validity [19]. Therefore, to simulate off-the-shelf conditions, no orientation or training related to MI product implementation was provided by the study team. Associated product orientation materials were provided to the teachers to review at their discretion one week prior to the intervention week. Teachers were allowed to determine the times and duration of product use and there were no restrictions or guidance from the research team. Teachers were informed that they were free to use any feature of the product to implement in their classroom as often or infrequently as they preferred. All teachers were informed of the study's purpose and that the study staff were not affiliated with the MI products. The three MI products were selected for this study because in a previous product

testing study conducted by our research team [20], teachers rated these products the highest and indicated that these products maximized facilitators of use while minimizing barriers to use.

Sample Size Considerations

A power analysis using G*Power (v.3.1.7) was performed to determine the sample size. With a power of 0.8 and an alpha of 0.05 and a sample of 60 teachers, the study had the ability to detect an effect size of 0.32 which translates to an 8.3 minute increase in MI use per day. This was deemed sufficient given past MI work showing similar increases in MI use per day [14, 21] and that 0.32 is commonly considered a small effect [22].

Movement Integration Products

ABC for Fitness is a free guidebook designed to provide teachers with ideas to intersperse physical activity bursts throughout the school day. Each activity burst has three components: A. Warm-up, B. Core Activity (e.g., exercise, stretching), and C. Cool Down lasting a maximum of five minutes. This resource contains academic content which teachers are encouraged to integrate into their lesson plans.

Take 10 is a classroom-based guidebook that provides teachers with grade-specific academic lessons that are integrated with PA. Each lesson offers an opportunity for the students to be physically active while learning academic content in one of five subject areas: language arts, math, science, social studies, or general health. Each activity is designed to last for a maximum of ten minutes. Take 10 employs a tiered pricing scheme based on grade level and ranges in cost from \$85-\$112.

GoNoodle is a free, online resource that contains a series of videos integrating grade-specific academic content with a variety of physical activities (e.g., dance, exercise, yoga) set to music

and activity breaks. These activities are non-teacher led and incorporate elements of social and emotional wellness to support child development. Video length tends to run between 5-10 minutes. For a cost (i.e., \$99 per year), GoNoodle Plus offers extended curricula videos, more learning games, and includes printable activities. Teachers were provided with the GoNoodle Plus version during product testing.

Outcomes

Teacher-reported MI strategy and MI Product use.

For each day that teachers participated in the study, they were asked to complete a daily log at the end of the school day indicating total uses of MI strategies (e.g., use of any MI product, provided or otherwise), uses of the specific MI product that they were provided, and the amount of time they used these products/strategies. In addition to use of the MI product, teachers were asked to provide information about their daily classroom schedule and out of classroom activities (e.g., physical education, recess, Art/Music, lunch). The log was collected from the teacher daily at the end of the school day by a trained research assistant.

Sedentary behaviors and Physical Activity.

Each teacher was observed on five school days during baseline and intervention weeks. In classrooms with 20 students or fewer (n=34) all students received an accelerometer. In classrooms with more than 20 students (n=23, mean number of students=24, SD=1.4) the first 20 students to arrive to school received an accelerometer each observation day. Random selection of students in classes with more than 20 students was not deemed necessary for because, this study focused on classroom level estimates of SB and PA, and classrooms with more than 20 students had a mean of 24 (SD=1.4) students. Thus, the vast majority of students were measured on any

given day. At the end of the school day, accelerometers were collected by trained research staff. Accelerometers (ActiGraph GT3X+ Shalimar, FL) were affixed to students' non-dominant wrist. Students' engagement in SB, light PA (LPA), and moderate-to-vigorous PA (MVPA) were calculated using previously developed cutpoint thresholds for elementary age children's sedentary behavior, LPA and MVPA [23]. Accelerometer epochs were set to five seconds to account for the intermittent and transitory nature of youth PA [24]. A valid day of accelerometer wear was defined as total time in attendance of at least 70% of the school day (260 mins) [25]. Age, sex, and race of all students were collected using school records.

Statistical analyses

Analyses were conducted on children that had at least one accelerometer wear day [26-28]. Descriptive means, standard deviations, and percentages (for dichotomous variables) were calculated for demographic characteristics, SB and PA, and teacher MI uses. Mixed effects general linear models were used to evaluate the impact of providing teachers access to MI products on their MI strategy use. Days measured were nested within teachers, and teachers were nested within schools. The dependent variables were number of overall MI strategy uses/day, the amount of time implementing MI per day, and the number MI product uses/day for the specific product provided. The independent variable was a dichotomous baseline or intervention week variable. To evaluate the impact of providing teacher access with MI products on students' SB and PA, mixed effects general linear models were estimated with days measured nested within children, children, nested within teachers, and teachers nested within schools. Separate models were estimated with SB, LPA, and MVPA as the dependent variables and the dichotomous baseline or intervention week variable as the independent variable. PA models controlled for

children's age (years), race, sex, and time in attendance at school. Additionally, all analytic models controlled for school day level factors (i.e., physical education vs. non-physical education day, recess vs. non-recess day).

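### Does the mismatch between 123 parental opt-outs and the stated 5.2% call for a change to the plan?

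*Combined protocol and SAP*

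**What the plan says.** Study setting and participants describes recruitment in the past tense. On teachers: "A total of 57 (60%) of teachers consented". On children: "For students in the consented teachers' classes, a passive consent procedure was employed", and "Letters with information about the study were sent home to the parents of children in the participating classes". The refusal figure follows: "A total of 123 (5.2%) parents opted out of their child wearing the activity monitor". No denominator is given for the 5.2%.

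Class sizes appear later, in the part of Outcomes on sedentary behaviours and physical activity: "In classrooms with 20 students or fewer (n=34) all students received an accelerometer", and "In classrooms with more than 20 students (n=23, mean number of students=24, SD=1.4". The two groups add up to 34 + 23 = 57 classes, one per consenting teacher.

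Two other statements bear on possible bases for the percentage. School-level data are said to be in a table ("Table 1 presents the participating schools' characteristics"), which is not in the text supplied for review; its absence is not a fault of the plan. Study design/procedure adds that, because of the pandemic, "we collected one baseline week and one intervention week in spring of 2020".

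**The concern.** The natural reading is that 123 of the children in the 57 classes were withheld and that this is 5.2% of them. The class sizes rule that out, because 5.2% would need more than 41 children in every class.

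This is the only parental-refusal figure in a study that used opt-out consent, in schools chosen because they serve many children with fewer opportunities to be active. A reader who wants to judge how well the monitored children represent their classes cannot tell whether roughly 1 in 20 or roughly 1 in 10 was withheld. If the higher rate is right, participation is less favourable than the text suggests.

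**Working it through.** **Inputs.** Opt-outs 123, stated as 5.2%; 57 teachers, stated as 60% (Study setting and participants). 34 classes of at most 20 children and 23 classes with a mean of 24 (Outcomes).

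**Base implied by the stated percentage.**
- 123/0.052 = 2,365 children.
- With 5.2% rounded from anywhere between 5.15% and 5.25%: 123/0.0525 = 2,343 to 123/0.0515 = 2,388.
- Per class: 2,365/57 = 41.5.

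**Most children the classes can hold.**
- 34 × 20 + 23 × 24 = 680 + 552 = 1,232.
- With the mean of 24 rounded from just under 24.5: 680 + 23 × 24.5 = 1,243.5.
- If the stated sizes leave out the 123 opted-out children: 1,232 + 123 = 1,355, or 1,243.5 + 123 = 1,366.5.

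These are ceilings, since every smaller class is set at 20. The ratio of implied base to ceiling runs from 2,343/1,366 = 1.7 to 2,365/1,232 = 1.9. The stated 5.2% is therefore not reproduced on this base.

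**What each figure would imply if the other were wrong.**
- 123 children correct: 123/1,366 = 9.0% to 123/1,232 = 10.0%. These are minimum rates, higher if the smaller classes average under 20.
- 5.2% correct: 0.052 × 1,232 = 64 children. If the class sizes exclude opted-out children, the upper value is 0.0525 × 1,243.5/0.9475 = 69.

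**Other bases that might give 5.2%.**
- *Enrolment of the five schools:* 2,365/5 = 473 per school. This cannot be checked without the table.
- *Classes of all teachers approached:* 57/0.60 = 95, so about 38 did not consent. Those classes would need (2,343 − 1,366)/38 = 25.7 children each, or (2,343 − 1,232)/38 = 29.2 if the stated sizes already include opt-outs. Their sizes are not given.
- *Individual parents, assuming two per child:* 2,365/2 = 1,183 children. With class sizes that include opt-outs, the smaller classes would average (1,183 − 552)/34 = 18.6, which is within their limit. The child-level rate would be 62/1,183 = 5.2% if both parents of each withheld child were counted, or 123/1,183 = 10.4% if one was.
- *Each child counted once in each of the two weeks:* the same arithmetic fits, although no text supports it.

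**Where the figure is used.** Sample Size Considerations works from 60 teachers, a power of 0.8, an alpha of 0.05 and an effect size of 0.32. Statistical analyses selects children by having at least one day of accelerometer wear and adjusts for age, race, sex, attendance time, and whether the day included physical education or recess. Neither section uses the opt-out count or percentage. The teacher outcomes come from daily logs and do not depend on which children wore a monitor.

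**Scale of any effect on representativeness.** Let p be the share withheld and δ the unknown difference in baseline-to-intervention change between withheld and monitored children. The whole-class mean change then differs from the monitored children's by p × δ. Moving p from 0.052 to 0.100 shifts that by (0.100 − 0.052) × δ = 0.048δ, about 5% of a gap that the study does not measure under either rate.

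**The case for a change.** The strongest case for acting is that the contradiction is certain on the natural reading and costs almost nothing to remove. The letters went only to families in the participating classes, so neither school enrolment nor the classes of all teachers approached is the right base. The opt-out form was to be signed by a parent and returned to the class teacher, which suggests one refusal per child and tells against counting two parents. Even if one of these bases lies behind the 5.2%, the sentence does not say so, and the child-level rate could be about half or about double what a reader assumes. In a study with opt-out consent, that rate ought to be stated correctly.

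Most of this stands: the denominator is unstated and does not match the class sizes. What does not follow is that 123 or 5.2% has been shown to be wrong, because the sentence counts parents and a parent-based reading reconciles both numbers. Nor does it follow that the plan needs changing. The correction would concern one descriptive sentence about recruitment that had already taken place; it would leave eligibility, measurement, analysis and interpretation of the effect as they are.

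**Conclusion.** The mismatch is genuine but clerical, and no change to the plan follows. Counting each child once, the stated percentage implies about 2,365 children, against a ceiling of about 1,232 to 1,366. The documents do not show whether the count, the percentage or the unstated base is responsible.

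The consequence is confined to a reported participation rate: 5.2% as stated, at least about 9 to 10% if 123 children is right, and about 5.2 to 10.4% if parents were counted at two per child. No model, outcome, selection rule or power figure depends on it, and no effect estimate would move. The study team holds the rosters and can state the denominator when reporting participation.

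This rests on three assumptions: one class per consenting teacher, which 34 + 23 = 57 supports; class sizes as given under Outcomes; and opted-out children wearing no monitor in either week, so that the choice to opt out does not by itself create a difference between the baseline and intervention weeks.

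### The valid-day rule and the time covariate both use school attendance, and no stated rule checks device wear, so off-wrist time may be scored as sedentary

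*Combined protocol and SAP*

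**What the plan says.** All references are to the combined protocol and SAP.

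- **Outcomes, Sedentary behaviors and Physical Activity (validity):** "A valid day of accelerometer wear was defined as total time in attendance of at least 70% of the school day (260 mins"). The quantity tested is presence at school.
- **Same section (device handling):** monitors "were affixed to students' non-dominant wrist". "At the end of the school day, accelerometers were collected by trained research staff".
- **Same section (processing):** SB, LPA and MVPA "were calculated using previously developed cutpoint thresholds for elementary age children's sedentary behavior, LPA and MVPA". "Accelerometer epochs were set to five seconds to account for the intermittent and transitory nature of youth PA". No other processing step is described.
- **Statistical analyses:** "Analyses were conducted on children that had at least one accelerometer wear day". The activity models adjust for "children's age (years), race, sex, and time in attendance at school", and the effect of interest is the coefficient of a baseline-or-intervention week indicator.
- **Study design/procedure:** there is no comparison group, and the baseline week comes before the product week.

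The plan gives no minimum wear time, non-wear detection rule or removal log, and does not say how runs of zero counts are scored.

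**The concern.** A monitor lying on a desk records counts at or near zero. A cutpoint method with no non-wear step puts those epochs below the sedentary threshold. Under the rule as written, a child who is at school all day but takes the monitor off still contributes a valid day. Fitting and collecting the device each day does not show that it was worn in between.

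The attendance covariate cannot repair this. Two child-days with the same attendance and different wear get the same adjustment.

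Two outputs are exposed. The first is the descriptive means of SB and activity, which any non-wear scored as SB would distort. The second is the week contrast. With no comparison group and a fixed order of weeks, a change in wear from the first week to the second falls entirely on the week coefficient. The school-level counterbalancing concerned the order of products, not the order of baseline and intervention.

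**Working it through.** **The plan's own figure.** The threshold is 260 min at 70% of the school day. The implied school day is 260 / 0.70 = 371.4 min, about 6.2 hours. That is plausible, but the documents give no school-day length, so 260 cannot be reproduced. No document figure exists for non-wear.

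**Model.** Let *A* be attended minutes, *s* the true SB share, *S* = *sA* the true SB minutes, and *w* the share of attended time off-wrist. Assume that all off-wrist time is scored as SB and that removed time has the same true SB share as the rest of the day. Then

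observed SB = *S*(1 − *w*) + *wA*, so the error in level is *wA*(1 − *s*).

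Off-wrist minutes that were truly sedentary are not misclassified, hence the factor (1 − *s*). LPA and MVPA together are too low by the same amount. *A* is taken as 371 or 260 from above; *s* = 0.50 and all values of *w* are assumptions.

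**1. Equal non-wear in both weeks**

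| *w* | SB level error, *A* = 371 | SB level error, *A* = 260 | Week contrast multiplied by (1 − *w*) |
|---|---|---|---|
| 5% | 0.05 × 371 × 0.5 = 9.3 min | 6.5 min | 0.95 |
| 10% | 18.6 min | 13.0 min | 0.90 |
| 30% | 55.7 min | 39.0 min | 0.70 |

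The levels move and the contrast shrinks. If the true change is zero, the contrast is not biased.

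**2. Unequal non-wear, no true change**

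Shift in SB change = (*w*₁ − *w*₀) × *A* × (1 − *s*).

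- 5% at baseline, 7% at intervention: 0.02 × 371 × 0.5 = +3.7 min (*A* = 260: +2.6).
- 5% at baseline, 10% at intervention: 0.05 × 371 × 0.5 = +9.3 min (*A* = 260: +6.5).
- A fall in non-wear of the same size gives the same shift with the opposite sign.

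**3. A milder pattern: some child-days with 60 minutes off-wrist**

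Shift = difference between weeks in the share of such child-days × 60 × (1 − *s*).

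| Difference in share | *s* = 0.50 | Upper limit, *s* = 0 |
|---|---|---|
| 2 points | 0.02 × 60 × 0.5 = 0.6 min/day | 1.2 |
| 5 points | 1.5 min/day | 3.0 |
| 10 points | 3.0 min/day | 6.0 |

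The upper limit applies only if none of the removed time was truly sedentary.

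**4. Against sampling error.** Assume a teacher-level SD of change of 5 to 10 min. With 57 teachers, SE = 5/√57 = 0.66 to 10/√57 = 1.32 min. The middle case is then 1.5/1.32 = 1.1 to 1.5/0.66 = 2.3 SE. This SE treats teachers as independent. Any school-level variation in change across the five schools would make it larger and these ratios smaller.

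**The case against.** A reader might infer that off-wrist time was counted as sedentary and that the SB, LPA and MVPA models are therefore biased. The documents do not support that. They are silent on how zero-count runs were scored, and a non-wear step may have been applied without being described. The cited sources for the cutpoints and the valid-day rule cannot be seen here. Nothing shows that children took monitors off: the devices were fixed to the wrist, used only in school hours and collected by staff. **This objection stands**, and it limits the point to what would follow from the rule as written.

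Attendance may also be a loose term for the period with the device on, since the sentence sets out to define a day of wear. This is possible, but less likely because the covariate in Statistical analyses is separately described as time in attendance at school.

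Bias in the contrast under no true effect needs non-wear to differ between weeks. **That stands.** The fixed order of weeks makes a difference possible; it supplies neither a direction nor evidence of one.

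A reader might also multiply the difference in share by the full 60 minutes and conclude that a 5-point difference is worth two or more standard errors. That treats every removed minute as truly active. At a 50% SB share the figure halves, and it reaches two standard errors only towards the lower end of the assumed SD range.

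Finally, the 70% threshold was stated for attendance, and applying it to wear is a choice that needs a reason. That is fair, and the fix allows for it.

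**Conclusion.** The point holds in a limited form. The plan states a concrete rule, and that rule never looks at the device signal. Followed as written with cutpoint scoring, it would inflate SB levels, lower LPA and MVPA levels, attenuate the week contrast under equal non-wear, and bias the contrast in either direction under unequal non-wear.

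The actual size is unknown. For modest differences in 60-minute removals the shift in SB change is about 0.6 to 3.0 min/day; for differences of 2 to 5 percentage points of all attended time it is about 2.6 to 9.3 min/day. Both ranges rest on assumed non-wear, a true SB share of 50%, and the scoring of all non-wear as sedentary. They show what the rule leaves open, not what happened in this study. Classed as a cheap improvement.

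**What to change.** 1. State whether non-wear was screened, and what time in attendance means. If a non-wear step was used, describe it.
2. If none was used, apply a non-wear algorithm to the recorded accelerometer data. Fix and state the length of the zero-count run before looking at the week contrast, and exclude the detected minutes from SB.
3. Define a valid day by detected wear minutes, for example at least 70% of the school day, with a reason for carrying that threshold over from attendance.
4. Use wear minutes in place of attendance as the covariate.
5. Report wear minutes by week, so that a reader can see whether wear differed.
6. Keep the attendance-based version as a sensitivity analysis.

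**Cost.** No new data collection: reprocessing of the recorded files, a refit of three models and small wording changes. This assumes that the files were kept, which the documents do not say. Some child-days would be lost, and some true stillness may be classed as non-wear. The shorter the run length, the more stillness is lost, which is why it must be stated.

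### Overall MI uses per day is a count fitted with a Gaussian mixed model that describes no teacher-level week effect: power may be lost, and intervals are too narrow if teachers respond differently.

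*Combined protocol and SAP*

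**What the plan says.** All three teacher outcomes share one model family: "Mixed effects general linear models were used to evaluate the impact of providing teachers access to MI products on their MI strategy use". The outcomes are listed as follows: "The dependent variables were number of overall MI strategy uses/day, the amount of time implementing MI per day, and the number MI product uses/day", where the last refers to whichever product the school was given. Two are therefore counts and one is a duration. The effect of interest is a single coefficient: "The independent variable was a dichotomous baseline or intervention week variable". The hierarchy is given as "Days measured were nested within teachers, and teachers were nested within schools", and the models also adjust for whether the day included physical education or recess.

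I read the model as Gaussian with an identity link, because no other distribution or link is named. The section describes no teacher-level variation in the week effect, no robust standard error and no residual check.

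On the amount of data: "Each teacher was observed on five school days during baseline and intervention weeks", "A total of 57 (60%) of teachers consented", and "Data were collected from five elementary schools in two separate school districts". Study design/procedure says that teachers had no training in the products from the study team and decided for themselves when, how long and how often to use them.

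**The concern.** Daily counts of classroom activities are small and non-negative, and their variance usually grows with their mean. A model with one residual variance gives heavy-using teachers, whose days are noisiest, the same weight per day as light users. That can cost power, and the number of teachers is fixed at 57.

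The second issue is separate. The planned model has one week effect for everybody. Where use is left to each teacher, some will probably take up a product and others ignore it. A model with only teacher and school intercepts puts most of that variation in response in the wrong place and reports a standard error that is too small for the average effect. Whether off-the-shelf products change what teachers do is the study's central behavioural question, so the interval around that change should be trustworthy.

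**Working it through.** **1. The plan's own figure.** Sample Size Considerations states a detectable effect of 0.32, equal to 8.3 minutes/day, with 60 teachers, power 0.8 and alpha 0.05. The implied SD is 8.3/0.32 = 25.9 minutes. A paired t-test with n = 60 and d = 0.32 has power 0.790 one-sided and 0.684 two-sided, so the figure reproduces only as a one-sided test. It concerns minutes, not counts, and does not depend on the point below.

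**2. Inputs.** From the documents: 57 teachers, and m = 5 days in each of two weeks. Assumed, because the documents give no mean, SD, zero share or dispersion for the counts: baseline mean 1 to 4 uses/day; negative binomial size 1 to 4, or Poisson; log-normal teacher rates with log-SD 0.5 to 1.0; and SD of the teacher-specific log response (tau) 0 or 0.4. School effects, covariates and missing days are left out.

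**3. Power with one rate ratio for all teachers (tau = 0), two-sided 0.05.** Simulated with 2,000 runs per row (1,200 for log-SD 1.0).

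| Mean | Size | Log-SD | Ratio | Gaussian | Neg. binomial | Gap (points) |
|---|---|---|---|---|---|---|
| 1 | 2 | 0.5 | 1.2 | 41.0% | 41.6% | 0.6 |
| 2 | 2 | 0.5 | 1.2 | 54.2% | 56.7% | 2.5 |
| 4 | 2 | 0.5 | 1.2 | 65.1% | 68.6% | 3.5 |
| 2 | 2 | 0.8 | 1.2 | 46.4% | 52.8% | 6.4 |
| 2 | 1 | 0.8 | 1.35 | 67.6% | 78.9% | 11.3 |
| 2 | 1.5 | 1.0 | 1.3 | 59.1% | 73.7% | 14.6 |
| 2 | Poisson | 0.8 | 1.2 | 88.2% | 87.4% | -0.8 |

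With no effect and tau = 0, the Gaussian model rejects in 4.5 to 5.6% of runs, so its size is sound there.

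**4. Why intervals become too narrow.** Let sw² be the average day-to-day variance within teacher and week, and sd² the variance between teachers in the true week difference. Per teacher:

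- true variance of the mean difference: V = 2·sw²/5 + sd²
- variance reported by a random-intercept model: V0 = 2·sw²/5 + sd²/9, because the variation in response is pooled into a residual with about 9 degrees of freedom per teacher
- type I error (or non-coverage) = 2[1 − Φ(1.96/√(V/V0))]

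*Example A* (mean 2, log-SD 0.5, size 2, no mean change, tau 0.4). The mean squared rate is 4e^0.25 = 5.136 at baseline and 5.136·e^0.16 = 6.027 in the intervention week. Then sw² = 2 + ½(5.136 + 6.027)/2 = 4.791 and sd² = 5.136(e^0.16 − 1) = 0.891. So V = 1.916 + 0.891 = 2.808 (unrounded inputs), V0 = 1.916 + 0.099 = 2.015, and √(V/V0) = 1.180. Type I error is 9.7%; simulation gave 10.3%.

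*Example B* (Poisson, mean 2, log-SD 0.8, no mean change, tau 0.4). The mean squared rate is 4e^0.64 = 7.586, sw² = 2, sd² = 7.586(e^0.16 − 1) = 1.316. So V = 2.116, V0 = 0.946, √(V/V0) = 1.495. Type I error is 19.0%; simulation gave 18.3%.

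*Example C* (Poisson, mean 2, log-SD 0.8, use doubles for everyone, tau 0). A common ratio still makes additive changes differ: sd² = 7.586 − 4 = 3.586, and sw² = 3. So V = 4.786, V0 = 1.598, √(V/V0) = 1.730. Coverage is 74.3%; simulation gave 74.2%.

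The shortfall comes from sd², the omitted teacher-by-week term.

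**5. Which analyses repair it (tau = 0.4, whole grid).**

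| Analysis | Type I error | Coverage of 95% interval |
|---|---|---|
| Gaussian, random intercept | 7.3–18.3% | 63–93% |
| Negative binomial, random intercept | 7.6–16.5% | 79–92% |
| Gaussian with week slope | 4.4–5.1% | 90–96% |
| Negative binomial, teacher-clustered SE | 5.2–7.8% | 90–95% |

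**6. Power of the two repaired analyses.** A separate check with 400 runs per scenario (standard error about 2 points) compared the clustered negative binomial with the Gaussian week-slope model: 71.5% vs 70.5% at log-SD 0.5, 72% vs 60% at log-SD 1.0, 80% vs 62% for a constant additive rise, and 76% vs 75% with Poisson counts. In the larger grid at tau = 0.4 the order varied: 31.1% vs 38.0% (mean 4, log-SD 0.5, size 2, ratio 1.2), but 84.4% vs 79.6% (mean 4, log-SD 0.8, size 4, ratio 1.35).

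**7. Provided-product uses.** Baseline use may be near zero. There are 57 × 5 = 285 baseline teacher-days. At an assumed 0.005 uses/day, the chance that all are zero is about e^(−1.425) = 24%, and a rate ratio then cannot be estimated.

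**The case against.** The best defence is that the planned model holds its size when teachers respond alike, gives the additive change in uses per day directly, and loses little power unless teachers differ widely and counts are overdispersed. That stands, and it limits the point to a cheap improvement.

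A reader might infer that the normal distribution causes the narrow intervals and that a negative binomial model would cure them. The documents do not support this. Step 4 traces the shortfall to the missing week slope, and step 5 shows that a random-intercept negative binomial model fails in much the same way. The freedom that Study design/procedure gives to teachers makes varying responses plausible.

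A reader might also infer that intervals fail whenever there is an effect. With a common ratio of 1.2, Gaussian coverage was about 94 to 96%. It falls clearly only for large effects (74 to 93% when use doubles), where the test decision is hardly in doubt.

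The target matters too. For the average change among the enrolled teachers only, Gaussian coverage was 94 to 97% at tau = 0 and 95 to 99% at tau = 0.4. These are volunteers in five purposively chosen schools, so that narrower target is defensible. However, the plan does not state it, and a random teacher level ordinarily implies inference beyond the sample.

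**Conclusion.** The concern holds in two parts, as a low-cost improvement. The plan analyses a daily count with a Gaussian mixed model and neither names a count model nor justifies the Gaussian one. The resulting power loss ranges from none to about 15 points. The upper end needs an assumed log-SD of 1.0 with overdispersed counts, so no single figure can be attached to this trial.

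The part that does not depend on model family is the absence of a teacher-level week effect or robust standard error. At an assumed log-response SD of 0.4, type I error for the mean change in a wider teacher population is roughly 7 to 18% with either family. Changing the family alone does not solve this, and adding the slope alone need not recover the lost power. Once response variation is handled, the negative binomial advantage is often present but not guaranteed (step 6).

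Two limits remain. Each school tested one product, so effects that differ by product or school add variance that was not simulated and that five schools can barely estimate. The sizing statement concerns minutes and is not touched by the choice of count model.

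**What to change.** - **Overall MI uses/day:** fit a negative binomial (log-link) mixed model with the same nesting and day-level covariates, plus a teacher-level random week slope or teacher-clustered robust standard errors. Report the rate ratio and the model-based difference in mean uses/day, with the Gaussian model as a sensitivity analysis. With a random slope, the ratio describes a typical teacher; at tau = 0.4 the ratio of means is larger by about e^0.08 = 1.08 if slope and intercept are uncorrelated. The mean difference should therefore be averaged over teachers.
- **Minutes/day:** keep the Gaussian model, also with a teacher-level week slope or clustered errors.
- **Provided-product uses:** report as uptake if baseline use is near zero.
- **Target:** say whether inference is to the enrolled teachers or to a wider population.

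The cost is small, since the data are already collected and standard software suffices. The downsides are a rate ratio as the direct coefficient, possible convergence work, intervals somewhat wider than those of the random-intercept model, and some residual size inflation with clustered errors (up to 7.8% in step 5).
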